## 11.2 Randomization

Eligible patients with an established diagnosis of pain and VOC will be consented and randomized to receive a single dose of gabapentin or placebo. Morphine or other opioid and non-steroidal anti-inflammatory drugs will be available to both groups as needed for pain and will be administered according to the current standard of care for pain in VOC from the Department of Hematology. Randomization will be performed in SJCRH pharmacy by a pharmacist, using the randomization program developed by the Department of Biostatistics. The randomization will be stratified by three age categories (1-3yr, 4-6yr,  $\geq 7$ yr) for which distinct pain assessment tools are applied and for 2 pain scores categories at assessment at presentation: 4- 6 and 7-10, respectively. A

block randomization with block sizes varying randomly between 4 and 6 will be used in each stratum.

### **11.3 Statistical analysis**

#### **11.3.1 Primary Objective**

To assess the analgesic efficacy of gabapentin (vs. placebo) for pain during VOC in participants with SCD. A response to study drug will be defined by a decrease in pain score of  $\geq 33\%$  between presentation to the acute care setting and assessment at 3 hours post administration of study drug.

For each patient, if the reduction of the pain scores between presentation to the acute care setting and 3 hours post administration of study drug is 33% or greater, then this patient will be defined as having a successful intervention. The proportions of successful interventions in the gabapentin and placebo groups will be estimated and compared using Z-test (PROC FREQ procedure in SAS).

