## **4.0 TREATMENT PLAN**

### **4.1 Treatment**

Upon each participant’s enrollment, study staff will randomize the participant to one of 2 possible treatment arms (see section 11 for randomization procedure) and order the study treatment. The pharmacy will dispense the dose of study treatment ( gabapentin vs. placebo) to the clinic or medicine room as soon as possible.

Study drug and other interventions will be administered and documented according to hospital policy by any appropriate clinical staff. All caregivers and study personnel will be blinded to the treatment assignment. Based on previous research experience at St. Jude, administration of the study drug is estimated to occur no later than 2 hours after patient’s first opioid pain medication in the acute care setting.

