## **6.2 Evaluations During Therapy**

Data for research purposes will be collected from the hospital medical records for the event, including visit duration, pain scores, and IV administered pain interventions given, as performed according to hospital standards of care. Only St. Jude pharmacists are unblinded to treatment assignment.

Pain assessments throughout the acute event will be performed by any clinical staff as per hospital standards (Appendix II). Researchers will analyze pain scores at baseline (at presentation), 15 minutes prior to or 15 minutes after the time of study drug administration, at 3 hours after study drug administration, and at point of decision for either admission or discharge to home (for patients who continue to be treated for pain longer than 3 hours after study drug is administered).

The pain scales used are the numerical rating system, the Faces Pain Scale, and the FLACC pain scale (for patients 7 years or older, ages 4-6 years, or less than 4 years, respectively) (Appendix II). Patients unwilling or unable to provide a score on the age-appropriate scale may use another scale if indicated.

Clinicians will obtain other studies as needed for good patient care.

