## APPENDICES

### APPENDIX I: Schedule of Evaluations (**required**)

Event	Screen 	Entry	On Treatment			24-72 hours after study drug
			Acute care setting	3 hours after study drug	Decision to discharge from acute care or admit	
Informed Consent	X					
Pregnancy test	PRN					
Pain assessment	X	X 	PRN	X	X 	
Study drug		X				
Pain intervention	PRN	PRN	PRN	PRN		
Adverse event screen				X	X	X
Off study						X

Routine pain interventions may begin before study entry/administration of study drug

Patients who leave the ACU at the 3 hour time point will not have a fourth pain assessment captured

Pain score will be recorded within 30 minutes of drug administration.

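### The primary Z-test ignores a dosing-time pain score that is already collected; adjusting for it would cost little and could sharpen the primary comparison

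*Combined protocol and SAP*

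**What the plan says.** Section 1.1 and section 11.3.1 define response from presentation to 3 hours after study drug. A patient is a success "if the reduction of the pain scores between presentation to the acute care setting and 3 hours post administration of study drug is 33% or" more. The two proportions "will be estimated and compared using Z-test (PROC FREQ procedure in SAS"), with no covariate named.

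Analgesia is not held back until dosing. Appendix I, footnote 1, states: "Routine pain interventions may begin before study entry/administration of study drug". Section 4.1 adds that "administration of the study drug is estimated to occur no later than 2 hours after patient’s first opioid pain medication in the acute care setting". That is an estimate, not a limit.

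A score around dosing is collected. Section 6.2 gives its window as "15 minutes prior to or 15 minutes after the time of study drug administration", whereas Appendix I, footnote 3, says: "Pain score will be recorded within 30 minutes of drug administration". In section 11.3.3 this score serves only exploratory objectives 4 and 5, as a numeric change and as a proportion of responders from dosing.

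Section 11.2 stratifies randomisation by three age groups and two bands of presentation score (4-6 and 7-10). Neither factor reflects what happens between presentation and dosing.

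**The concern.** The primary window opens before study drug is given. If dosing follows the first opioid by the estimated maximum of 2 hours, the time from first opioid to the primary assessment is about 2 + 3 = 5 hours, of which about 2 precede study drug.

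Take a child who arrives at 8, has fallen to 4 after opioid by dosing, and is still at 4 three hours later. From presentation the fall is (8 - 4)/8 = 50%, a success. From dosing it is (4 - 4)/4 = 0%. The child is a success in either arm, whatever study drug did.

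Such patients add variation unrelated to treatment. Part of it is visible in the dosing-time score. Section 5.1 cites a mean time to peak concentration of 2.31 hours, so a score taken around dosing is essentially pre-treatment and is a reasonable covariate. At stake is how much information the 166 patients yield, not whether the comparison is valid.

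**Working it through.** **1. Reproduce the planned power (section 11.1).** Inputs: 45% against 65%, 83 per arm, one look at 96 patients (48 per arm), and one-sided nominal p-values of 0.0143 (efficacy), 0.2249 (futility) and 0.0447 (final).

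- Variance term: 0.45 x 0.55 + 0.65 x 0.35 = 0.475.
- Expected Z at the look: 0.20 / sqrt(0.475/48) = 2.01.
- Expected Z at the end: 0.20 / sqrt(0.475/83) = 2.64.
- Correlation of the two statistics: sqrt(96/166) = 0.76.
- Bivariate normal result: power 80.2% if the futility rule is obeyed; overall one-sided type I error 0.0500 if it is ignored (it is non-binding). A binomial simulation with the pooled Z-test gives 81%.

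The stated design reproduces.

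**2. Check which scale the planning figures use.** The 45% is 18/40 opioid-treated patients, measured from baseline to discharge or admission. It therefore already contains opioid relief, although its end point is the end of the visit and not 3 hours after dosing. The 20-point gain is also stated from presentation.

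Power falls only if a different alternative is assumed. Let q be the share already at 33% relief by dosing, and suppose they stay responders in both arms. Suppose also that gabapentin adds 20 points only among the rest. The overall difference is then 0.20 x (1 - q). The documents do not give q, so the range is an assumption.

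| Assumed q | Overall difference | Power, planned boundaries | Gain needed among the rest for 65% overall: 0.20/(1 - q) |
|---|---|---|---|
| 0 | 20 points | 81% | 20 points |
| 10% | 18 points | 73% | 22 points |
| 20% | 16 points | 64% | 25 points |
| 30% | 14 points | 55% | 29 points |

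This shows what a smaller overall effect would cost. It is not an error in the sample size.

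**3. What would using the score gain on the planned scale?** Here the overall rates stay at 45% and 65%, with 83 per arm, one-sided 0.0447 and no interim look. The unadjusted Z-test then has about 83-84% power in simulation.

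*(a) Two strata: already at 33% relief by dosing, or not.* A second unknown enters: the share of already-improved placebo patients who are still responders at 3 hours (persistence, p). Placebo response among the rest is (0.45 - q x p)/(1 - q). For q = 20% and p = 90% that is (0.45 - 0.18)/0.80 = 34%. A common odds ratio was set to give 65% overall. The Mantel-Haenszel test changes power as follows:

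- q = 10%: between about -1 and +1 point.
- q = 20% or 30% with persistence of 60-70%: about nil, from slightly negative to about +1.
- q = 20% with persistence of 80-90%: about +2 to +4 points (85-87%).
- q = 30% with persistence of 80-90%: about +4 to +7 points (88-91%).

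*(b) The score as a continuous covariate.* Fit a logistic model for response on arm and score, average each patient's predicted risk under each arm, take the difference, and use a robust variance. With response modelled as a threshold on a normal scale, the gain is between nil and 1 point at an assumed correlation of 0.3, about 4 points at 0.5 and about 10 points at 0.7.

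Under no treatment effect, the rejection rates of the stratified and adjusted tests stay near the nominal 4.5%.

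The continuous covariate is the better choice, because a single cut at 33% discards information and at low q can lose a little power.

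**The case against.** The strongest case for leaving the plan alone has four parts.

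- **The endpoint suits the question.** The trial asks whether gabapentin helps when added to standard care, so total relief from presentation is a legitimate outcome. This stands, and the endpoint should stay.
- **The dosing-time contrast will be seen anyway.** Exploratory objective 4 reports it. That is true, so nobody should infer that the score goes unused. But an exploratory result cannot sharpen the primary test. A baseline taken at dosing may also be low or zero, which makes a 33% fall unstable or undefined. Used as a covariate, the score avoids this.
- **The gain rests on unsourced assumptions.** This also stands. The documents do not give the share improved by dosing, how long that relief lasts, or any correlation.
- **The score is awkward.** It is recorded after randomisation, may fall slightly after dosing, has two stated windows, and will not exist for a randomised patient who is not dosed. The boundaries were also built for an unadjusted comparison. These points can be handled, but they must be written down.

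Two stronger readings are tempting. A reader might infer that opioid relief before dosing biases the result towards gabapentin. The documents do not support this: allocation is randomised and blinded, so such relief is expected equally in both arms. A reader might also infer that the trial is underpowered. The planning rate and the target gain both sit on the from-presentation scale, and the stated power reproduces. The losses in step 2 come only from assuming a smaller effect.

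Nor does the score isolate the drug's effect fully. Earlier opioids may still be acting after dosing, and later opioids count under any baseline.

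**Conclusion.** This is a cheap improvement, not a flaw that threatens the conclusion. The primary endpoint includes relief obtained before study drug, and the unadjusted Z-test leaves aside a score, already collected, that is likely to explain part of that relief. The comparison is unbiased and the 80% power holds as planned.

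The benefit is precision. It is about nil if few patients improve before dosing or the improvement fades, and roughly 1 to 10 power points at assumed correlations of 0.3 to 0.7. That the score predicts the outcome is a reasonable expectation, not something the documents show. Calling the outcome a response to study drug is loose wording, but the operational definition that follows is explicit, so relabelling would be cosmetic.

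**What to change.** Keep the endpoint and amend section 11.3.1 before any unblinded look:

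1. Make the primary comparison a regression-standardised risk difference with robust variance. Adjust for the dosing-time score (or the percent change from presentation to dosing), age group and presentation score. The last two are the randomisation factors, which the Z-test also omits.
2. Use the same statistic at the 96-patient look and at the final analysis. The boundaries are nominal p-values and can be carried over, but their operating characteristics should be confirmed for the adjusted test.
3. Report the unadjusted Z-test as a sensitivity analysis.
4. Use the last score at or before dosing where there is one. Reconcile the 15-minute window in section 6.2 with the 30-minute window in Appendix I.
5. Keep patients with no dosing-time score, including any not dosed, in the intention-to-treat analysis through a missing indicator.
6. Tabulate by arm the share already at 33% relief or more at dosing.

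No new data, visits or patients are needed. The cost is a few lines of analysis plan, a little more programming and a missing-data category.

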respectively. We wish to test whether there is a significant difference in the proportions of participants with a decrease of  $\geq 33\%$  in pain scores in two groups and formulate the following hypothesis: the null hypothesis  $H_0: \Delta = P_t - P_c = 0$  against the 1-sided alternative hypothesis  $H_1: \Delta > 0$ . With the design parameters of a type I error rate ( $\alpha$ ) of 0.05 and a type II error rate ( $\beta$ ) of 0.2, assuming one interim analysis and  $\Delta = 0.2$  under  $H_1$ , we will need a total of 166 patients (83 per group) for our two sample test. The interim analysis will be conducted to assess efficacy and futility, when there are 96 subjects randomized. We will recommend that the trial will be halted for efficacy (in favor of  $H_1$ ) if the nominal p-value for the interim analysis is less than or equal to 0.0143. We will recommend the trial should be halted for futility (in favor of  $H_0$ ) if the nominal p-value for the interim analysis is greater than or equal to 0.2249. If  $H_0$  is true, this interim analysis has a 79% probability of stopping in favor of  $H_0$ . If  $H_1$  is true, this interim analysis has a 53% probability of stopping in favor of  $H_1$ . To account for the planned interim analysis, the final analysis will be at the nominal p-value of 0.0447; thus maintaining the overall type I error rate at 0.05. This plan is based on the binomial two-sample difference in proportions with a non-binding interim analysis based on power family spending functions with alpha and beta spending parameters set to 0.1 (EAST software v5.3).

**Accrual:** Based on the retrospective data, we can expect to prospectively evaluate 63 patients for enrollment per year. If we enroll and randomize 2/3 of the eligible patients, the enrollment would reach 42 patients per year. Therefore, it will take approximately four years to enroll all 166 patients necessary to address the primary objective.

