#### **11.3.3 Exploratory Objectives**

1. To assess the analgesic efficacy of gabapentin for pain during VOC in participants with SCD, as defined by a decrease in pain scores of  $\geq 33\%$

between presentation to the acute care setting and the point of decision for either hospital admission or discharge to home, in the gabapentin and placebo groups.

Statistical methods used to analyze this objective will be the same as those used for the primary objective.

2. To compare the total morphine dose or morphine equivalent (mg/kg) used to control pain during VOC between presentation to the acute care setting and the point of decision for either admission or discharge to home, in the gabapentin and placebo groups.

Statistical methods used to analyze this objective will be the same as those used for the secondary objective.

3. To compare the rate of admission related to pain management, in the gabapentin vs. placebo groups.

Statistical methods used to analyze this objective will be the same as the analysis used for the primary objective.

4. To compare the change in pain score from time of administration of study drug to assessment at 3 hours post administration of study drug in the gabapentin vs. placebo groups.

The numeric changes in pain scores will be compared using the statistical methods of the secondary objective. Changes in pain score will also be evaluated as a proportion of those with a decrease of  $\geq 33\%$  and analyzed by the methods of the primary objective.

5. To compare the change in pain score from time of administration of study drug to the point of decision for either admission or discharge to home, in the gabapentin and placebo groups.

The numeric changes in pain scores will be compared using the statistical methods of the secondary objective. Changes in pain score will also be evaluated as a proportion of those with a decrease of  $\geq 33\%$  and analyzed by the methods of the primary objective.

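### The primary Z-test ignores the six randomisation strata; a prespecified stratified test would hold the error rate near 0.05, at about -1 to +2 points of power unless the strata are strongly prognostic

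*Combined protocol and SAP*

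**What the plan says.** Section 11.2 states "The randomization will be stratified by three age categories" (1-3, 4-6 and 7 years or older), "for which distinct pain assessment tools are applied and for 2 pain scores categories at assessment at presentation" (4-6 and 7-10). That makes 3 × 2 = 6 strata, and "block sizes varying randomly between 4 and 6 will be used in each stratum".

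Section 11.3.1 defines success as a fall in pain score of at least 33% from presentation to 3 hours after study drug. The proportions in the two arms "will be estimated and compared using Z-test (PROC FREQ procedure in SAS"). No stratification factor, CMH test or adjusted model is named.

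Section 11.3.3 carries the same test over to the exploratory binary outcomes. For response at the decision point it says "Statistical methods used to analyze this objective will be the same as those used for the primary objective", and admission is handled likewise. For objectives 4 and 5, "Changes in pain score will also be evaluated as a proportion of those with a decrease of" 33% or more, again by the primary method.

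The sample size in Section 11.1 is unstratified too: "This plan is based on the binomial two-sample difference in proportions". On timing, "The interim analysis will be conducted to assess efficacy and futility, when there are 96 subjects randomized".

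**The concern.** Blocking within strata balances the arms on age group and presentation pain. If those factors predict response, the true variance of the difference in proportions is smaller than the variance an unstratified Z-test assumes. The test is then conservative by an amount that depends on how prognostic the strata are.

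The endpoint gives some reason to expect an effect. On a whole-number 0-10 scale, a fall of at least 33% means 2 points from a score of 4, 5 or 6, 3 points from 7, 8 or 9, and 4 points from 10. The stratum cut between 6 and 7 is where the required fall first changes. The age groups were chosen because they use different pain tools. Both stratification factors therefore bear on how response is measured.

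At stake is whether the error rate that Section 11.1 sets at 0.05 is actually delivered, together with a little power. The validity of the trial is not in question.

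**Working it through.** **1. Reproduce the plan (Section 11.1).** Inputs: 45% vs 65%, 83 per arm, look at 96 (48 per arm), one-sided boundaries p ≤ 0.0143 (efficacy), p ≥ 0.2249 (futility, non-binding) and p ≤ 0.0447 (final).

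- Boundaries as z: 2.189, 0.756 and 1.699. Correlation between looks: √(96/166) = 0.760.
- Expected z = 0.20 / √[(0.45×0.55 + 0.65×0.35)/n] = 0.20 / √(0.475/n). This is 2.01 at n = 48 and 2.64 at n = 83.
- Bivariate normal result: overall error 0.0500 with futility ignored; power 0.801 with futility obeyed. The plan's 0.05 and 80% reproduce.

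**2. Define how prognostic the strata are.** R² = between-stratum variance of placebo response / (0.45 × 0.55). The protocol gives neither stratum sizes nor stratum response rates. The 45% planning rate comes from 40 patients aged 8-18, all in the oldest stratum. R² is therefore an assumption, shown from 0 to 0.26.

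**3. Simulate both tests under the planned randomisation.** N = 166, look at 96, the boundaries above, permuted blocks of 4 or 6 in each of six strata, 50,000-60,000 trials per setting. CMH has no continuity correction and merges ages 1-3 and 4-6 within each pain category, giving four strata. Type I error ignores futility; power obeys it. Ranges cover two assumed mixes (A: ages 15/20/65%, pain 40/60%; B: ages 5/10/85%, pain 30/70%), stratum effects by pain alone or by pain and age, and a treatment effect constant on the logit or the risk-difference scale. R² of 0.02, 0.06 and 0.26 used pain-only, logit effects. Monte Carlo SE is about 0.001 for error and 0.002 for each power.

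| Stratum R² | Z-test overall error | CMH minus Z, power (points) |
|---|---|---|
| 0 | 0.054-0.055 | -1.1 to -1.3 |
| 0.02 | – | -0.8 to -0.9 |
| 0.05 | about 0.050 | -0.1 to -0.4 |
| 0.06 | – | 0 to -0.1 |
| 0.10 | 0.045-0.047 | +0.5 to +1.2 |
| 0.13 | – | +1.2 to +1.8 |
| 0.20 | 0.036-0.037 | +2.3 to +3.5 |
| 0.26 | – | +3.4 to +3.7 |

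Four-stratum CMH error is 0.048-0.052 throughout. Z-test power is 80.5-80.7% at R² 0 and 82.7-83.7% at 0.20.

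Part of the CMH loss at R² 0 arises because the Z-test runs slightly above 0.05 there. With both tests calibrated to a true error of 0.050, power is 79.3% (Z) vs 79.1% (CMH) in mix A and 79.4% vs 79.1% in mix B, a cost of 0.2-0.4 points allowing for rounding.

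**4. Translate R² into response rates.** If pain category alone carries the effect, the gap in placebo response is √[R² × 0.45 × 0.55 / (f(1-f))], where f is the share with pain 4-6. With f = 0.40 and R² = 0.05: √(0.012375/0.24) = 0.227, so the rates are 0.45 + 0.6×0.227 = 59% and 0.45 - 0.4×0.227 = 36%. R² 0.10 needs 64% vs 32%, and R² 0.20 needs 72% vs 27%. With f = 0.30 the three pairs are 62/38%, 69/35% and 79/30%.

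**5. What the endpoint definition implies.** Take a normally distributed change with SD 2-3 points, 30-50% of patients at pain 4-6 and 45% overall response. Pain category then gives R² of about 0.002 if the average fall is proportional to the starting score, and up to about 0.06 if it is the same number of points for all. The age/instrument contribution cannot be derived.

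**6. Six strata instead of four.** At R² 0 the cost is -1.3 to -1.7 points. The chance that some stratum has an empty arm at the interim is 5% (mix A) or 83% (mix B) with six strata, against 0% or 15% with four. A separate six-stratum simulation with other mixes (8,000-10,000 trials per scenario) shows the same pattern: CMH error 0.047-0.054 and power -1.2 to -1.6 points when strata do not matter. With an odds ratio of 3 per factor the change is +0.7 to +1.0, and with 5 it is +2.3 to +2.8.

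**The case against.** The strongest reply is that the planned test is valid, prespecified and matched to the sample-size calculation, and that the only stratum effect derivable from the protocol (R² about 0.002-0.06) puts the change at about -1 to 0 points of power. Break-even needs roughly 59% vs 36% placebo response between pain categories, a gap wider than the 20-point treatment effect. If the strata do not matter, CMH power is about 79.2-79.6% (80.5-80.7% less 1.1-1.3), just under the planned 80%. All of that stands. It rules out presenting the change as a power gain, though most of the shortfall at R² 0 disappears when the two tests are compared at equal true error.

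Merging ages 1-3 and 4-6 pools two pain instruments, so the recommended test does not use every randomisation stratum. That is a fair point, and the price of avoiding empty cells at the interim. Even then, mix B leaves a 15% chance of an empty arm in some stratum, and CMH gives such a stratum no weight.

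The simulations cover the primary endpoint only. For the exploratory outcomes the recommendation rests on consistency. The text to be changed also sits in the protocol, so the edit needs the usual protocol review.

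None of this shows the stratified test to be unsound, or removes the dependence of the Z-test's error rate on an unknown stratum effect.

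**Conclusion.** The concern holds as a low-severity improvement whose main benefit is calibration. Between R² 0 and 0.20 the Z-test's overall error moves from about 0.055 to about 0.037, while four-stratum CMH stays within 0.048-0.052. The power change is about -1 to +2 points up to R² 0.13, and exceeds +2 only when strata explain around 20% or more of the variance in response. The Z-test keeps at least 80% power across the range examined. These figures rest on assumed stratum mixes and effects, so confidence in the size is medium. The omission itself is plain in the text.

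**What to change.** Before the 96-patient interim and any unblinding, amend Section 11.3.1 so that the primary analysis is a CMH test with a Mantel-Haenszel risk difference and confidence interval, at the same one-sided thresholds (0.0143, 0.2249 and 0.0447). Use four strata at both looks: ages 1-3 and 4-6 merged within each pain category. Fix the merge in advance and do not decide it from observed counts. Keep the Z-test as a sensitivity analysis, and apply the same method to the exploratory binary outcomes in Section 11.3.3.

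State the downside in the plan: about 1-1.5 points of power if the strata do not predict response, and a slight departure from the unstratified calculation in Section 11.1. The cost is analysis wording and its review. PROC FREQ, already named, has a CMH option, and the strata are recorded at randomisation, so no new data or patients are required. Making the choice after seeing unblinded data would not be credible.
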